Subjects who meet all of the eligibility criteria will be randomized to one of six treatment sequences as described in [Figure 3-1](#). They will receive their first dose on the morning of Day 1. Subjects will be dosed between 06:00 a.m. and 10:00 a.m. under the guidance and supervision of the investigator or designee after an additional training for correct use of the Concept1 inhalation device. Dosing of investigational product and background ICS medication should occur at approximately the same time of the day throughout the study. For details of administration of investigational product please refer to [Section 6.5](#). PEF measurements (if not already performed at home on the morning of Day 1 or Day 14) should be taken prior to pre-dose spirometry and safety assessments

For further details, refer to the [Assessment schedule](#).

On Day 1, subjects will leave the clinic after the completion of the required assessments and will dose at home once daily in the morning on Days 2 to 13. During days 2 -13, subjects will record drug administration, PEF measurements, mouth rinsing, and rescue medication use in their diary. Subjects will be domiciled at the clinic on the morning of Day 14, for drug administration and Day 14 visit assessments. For details, refer to the [Assessment schedule](#). Subjects will be discharged on Day 15 following the final PK and safety blood sample draw and completion of Day 15 assessments.

A washout period of 7 - 14 days will separate each treatment period. Apart from the pre-dose spirometry and safety assessments on Day 1 which will only be done before Treatment period 1, the assessments for Treatment Periods 2 and 3 will be identical to Treatment period 1 (refer to the [Assessment schedule](#) for Treatment periods 2 and 3 assessments).

Epoch Completion assessments must be conducted for subjects who complete all three treatment periods or at any time a subject early terminates from the trial. The last visit (Day 65) of Treatment period 3 will also be the end of study visit. For assessments that are listed in both Day 65 and in Epoch completion, the assessment is to be completed once. Subjects should be discharged from the site after the completion of Day 15 assessments for all 3 periods. Serious Adverse Event (SAE) reporting after the End of Study visit is described in [Section 9.2.2](#) (SAE reporting).

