3.2 Rationale of study design

Long action β_2 agonists are recommended in asthmatics not adequately controlled with ICS alone. In addition, long-acting β_2 agonists are not recommended in asthmatics without ICS background therapy. Therefore subjects with asthma requiring daily treatment with an ICS (i.e. maintenance treatment) to achieve control have been specifically selected for this study.

A 14-day treatment crossover design is chosen to characterize lung function effects of once daily indacaterol maleate and indacaterol acetate compared to placebo in subjects with asthma. Bronchodilator effects of indacaterol are expected to reach steady state with no additional improvements in lung function after 14 days of treatment. For further details please refer to [Section 3.3](#).

The crossover design has been selected for this study as the intra-subject variability of the primary endpoint (FEV₁) is lower than the inter-subject variability in this patient population thereby allowing the total number of subjects studied to be minimized without impacting statistical power. The utilization of a Williams design is efficient with the use of six sequences of seven subjects/sequence allowing balance for first order carryover. For once daily dosing regimens of indacaterol, the effective half-life of accumulation (T_{1/2,acc}), of indacaterol ranges from 40 to 56 hours. Therefore, the maximum expected washout period based on T_{1/2,acc} would need to be approximately 12 days [(5 x T_{1/2})/24]. As pharmacokinetic assessments will only be completed at steady state i.e. at the end of each treatment period, the duration between PK assessments in successive treatment periods in this study will be effectively 21 to 28-days (14 days treatment periods separated by 7-14 day washout periods). In addition, this washout is considered appropriate with regards to the measured primary PD effect (trough FEV₁), with the effect of indacaterol on FEV₁ lasting for approximately 48-hours after the last dose (Study CQAB149B2223).

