7.1 Study completion and post-study treatment

Each subject will be required to complete the study in its entirety and thereafter no further study treatment will be made available to them.

Study completion is defined as when the last subject completes their Study Completion visit, and any repeat assessments associated with this visit have been documented and followed-up appropriately by the investigator, or in the event of an early study termination decision, the date of that decision.

All subjects should have a safety follow-up call conducted 30 days after last visit. The information collected is kept as source documentation. All SAEs reported during this period must be reported as described in [Section 9.2](#) and the Site Operations Manual. Documentation of attempts to contact the subject should be recorded in the source documentation.

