- Clinical asthma worsening which required additional asthma treatment other than study medication or study-defined rescue medication in any one treatment period.

If a liver event occurs, follow guidelines outlined in [Appendix 1](#) regarding discontinuation of study treatment.

Any of the following laboratory abnormalities:

- Random (non-fasting) plasma glucose greater than 15 mmol/L
- Serum potassium below the lower limit of the laboratory reference range if confirmed by a repeat test to exclude laboratory error
- Urine cotinine $>$ than the laboratory's lowest level of quantification (LoQ of 500 ng/mL or lower) after randomization (a positive test at screening would preclude inclusion into the study)

Discontinuation of study treatment and subject withdrawal will be at the discretion of the investigator, under the following circumstances:

- Clinically significant abnormal laboratory value(s) (as judged clinically significant by the investigator).
- The investigator deems discontinuation is necessary for the safety of the patient.

The appropriate personnel from the site and Novartis will assess whether study treatment should be discontinued for any subject whose treatment code has been broken inadvertently for any reason.

If discontinuation of study treatment occurs, investigator must determine the primary reason for the subject's premature discontinuation of study treatment and record this information on the Dosage Administration eCRF.

Subjects who discontinue study treatment or who decide they do not wish to participate in the study further should not be considered withdrawn from the study unless they withdraw their consent (see [Section 7.3](#)). Where possible, they should return for the assessments conducted on Day 15/End of Study Visit. If they fail to return for these assessments for unknown reasons, every effort (e.g. telephone, e-mail, letter) should be made to contact the subject/pre-designated contact as specified in [Section 7.4](#). (Lost to follow-up). This contact should preferably be done according to the study visit schedule.

After study treatment discontinuation, at a minimum, in abbreviated visits, the following data should be collected at clinic visits or via telephone/email contact until the subject's end of study visit:

- new /change in concomitant treatments
- adverse events/serious adverse events

The investigator must also contact the IRT to register the subject's discontinuation from study treatment.

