9.1 Adverse events

An adverse event (AE) is any untoward medical occurrence (i.e., any unfavorable and unintended sign including abnormal laboratory findings, symptom or disease) in a subject or clinical investigation subject *after providing written informed consent* for participation in the study until the end of study visit. Therefore, an AE may or may not be temporally or causally associated with the use of a medicinal (investigational) product.

In addition, all reports of intentional misuse and abuse of the study treatment are also considered an adverse event irrespective if a clinical event has occurred. See [Section 9.5](#) (Reporting Medication errors including misuse/abuse) for an overview of the reporting requirements.

The occurrence of adverse events must be sought by non-directive questioning of the subject at each visit during the study. Adverse events also may be detected when they are volunteered by the subject during or between visits or through physical examination finding, laboratory test finding, or other assessments.

Abnormal laboratory values or test results constitute adverse events only if they fulfill at least one of the following criteria:

- they induce clinical signs or symptoms,
- they are considered clinically significant,
- they require therapy.

Clinically significant abnormal laboratory values or test results should be identified through a review of values outside of normal ranges/clinically notable ranges, significant changes from baseline or the previous visit, or values which are considered to be non-typical in subjects with underlying disease. Investigators have the responsibility for managing the safety of individual subjects and identifying adverse events. Alert ranges for liver related events are included in [Section 15-Appendix 1: Liver Event Definitions and Follow-up Requirements](#)). Adverse events must be recorded on the Adverse Events CRF under the signs, symptoms or diagnosis associated with them, and accompanied by the following information:

- the severity grade
 - mild: usually transient in nature and generally not interfering with normal activities
 - moderate: sufficiently discomforting to interfere with normal activities
 - severe: prevents normal activities
- its relationship to the study treatment
 - study treatment (no/yes), or
 - other treatment (no/yes), or
 - both or indistinguishable

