- its duration (start and end dates) or if the event is ongoing an outcome of not recovered/not resolved must be reported.
- whether it constitutes a serious adverse event ([Section 9.2.1 \(Definition of SAE\)](#)) and which seriousness criteria have been met
- action taken regarding investigational treatment

All adverse events must be treated appropriately. Treatment may include one or more of the following:

- no action taken (e.g. further observation only)
- investigational treatment dosage adjusted/temporarily interrupted
- investigational treatment permanently discontinued due to this adverse event
- concomitant medication given
- non-drug therapy given
- subject hospitalized/subject's hospitalization prolonged ([Section 9.2.1 \(Definition of SAE\)](#))
- its outcome (not recovered/not resolved; recovered/resolved; recovering/resolving, recovered/resolved with sequelae; fatal; or unknown)

Information about common side effects already known about the investigational drug can be found in the IB. Once an adverse event is detected, it must be followed until its resolution or until it is judged to be permanent, and assessment should be made at each visit (or more frequently, if necessary) of any changes in severity, the suspected relationship to the investigational drug, the interventions required to treat it, and the outcome.

The investigator must also instruct each subject to report any new adverse event (beyond the protocol observation period) that the subject, or the subject's personal physician, believes might reasonably be related to study treatment. This information must be recorded in the Investigator's source documents; however, if the AE meets the criteria of an SAE, it must be reported to Novartis.

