
9.2.2 SAE reporting

To ensure subject safety, every SAE, regardless of causality, occurring after the subject has provided informed consent and until 30 days after the last IP administration, must be reported to Novartis **within 24 hours of learning of its occurrence** as described below. Any SAEs experienced after this period should only be reported to Novartis if the investigator suspects a causal relationship to study treatment.

All follow-up information for the SAE including information on complications, progression of the initial SAE and recurrent episodes must be reported as follow-up to the original episode within 24 hours of the Investigator receiving the follow-up information. An SAE occurring at a different time interval or otherwise considered completely unrelated to a previously reported one must be reported separately as a new event.

Follow-up information provided must describe whether the event has resolved or continues, if and how it was treated, whether the blind was broken or not (if applicable) and whether the subject continued or withdrew from study participation. Each re-occurrence, complication, or progression of the original event must be reported as a follow-up to that event regardless of when it occurs.

If the SAE is not previously documented in the IB or Package Insert (new occurrence) and is thought to be related to the study treatment a Drug Safety and Epidemiology Department associate may urgently require further information from the investigator for Health Authority reporting. Novartis may need to issue an IN to inform all investigators involved in any study with the same study treatment that this SAE has been reported. Suspected Unexpected Serious Adverse Reactions (SUSARs) will be collected and reported to the competent authorities and relevant ethics committees in accordance with EU Guidance 2011/C 172/01 or as per national regulatory requirements in participating countries.

Follow the detailed instructions outlined in the Site Operations Manual regarding the submission process for reporting SAEs to Novartis. **SAEs must be reported to Novartis within 24 hours** of the investigator learning of its occurrence/receiving follow-up information.

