Adverse events

All information obtained on adverse events will be displayed by treatment and subject.

All treatment emergent adverse events will be summarized. Adverse events starting on or after the time of the first inhalation of study drug will be classified as a treatment emergent adverse event. Any adverse events that started during a washout period will be assigned to the treatment period just prior to that washout period. Any adverse events that started during the study before the time of the first inhalation of study drug of the first period will be classified as a prior adverse event and will not be summarized.

The number and percentage of subjects with treatment emergent adverse event will be summarized by treatment, overall by system organ class and preferred term, overall by system organ class, preferred term and maximum severity, suspected drug-related adverse events by system organ class and preferred term, serious adverse events by system organ class and preferred term, and adverse events leading to permanent discontinuation of study drug by system organ class and preferred term with a breakdown by treatment. A subject with multiple adverse events within a body system and treatment period is only counted once towards the total of this body system and treatment.

For the legal requirements of ClinicalTrials.gov and EudraCT, two required tables on treatment emergent adverse events which are not serious adverse events with an incidence greater than 5% and on treatment emergent serious adverse events and SAE suspected to be related to study treatment will be provided by system organ class and preferred term on the safety analysis set population.

If for a same patient, several consecutive AEs (irrespective of study treatment causality, seriousness and severity) occurred with the same SOC and PT:

- a single occurrence will be counted if there is ≤ 1 day gap between the end date of the preceding AE and the start date of the consecutive AE
- more than one occurrence will be counted if there is > 1 day gap between the end date of the preceding AE and the start date of the consecutive AE.

For occurrence, the presence of at least one SAE / SAE suspected to be related to study treatment / non SAE has to be checked in a block e.g., among AE's in a ≤ 1 day gap block, if at least one SAE is occurring, then one occurrence is calculated for that SAE.

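### Adverse events reach the analysis for only about one day after the last Period 3 dose, but for the whole washout after Periods 1 and 2, which understates late non-serious events for every treatment

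*Protocol*

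**What the plan says.** **Where collection ends.** Protocol 9.1 defines an adverse event (AE) as an untoward occurrence after written consent "for participation in the study until the end of study visit". Section 3.1 states: "The last visit (Day 65) of Treatment period 3 will also be the end of study visit". Table 8-1 puts the last Period 3 dose on Day 64, and its footnote 3 provides no washout after that period.

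**Periods 1 and 2.** Footnote 3 sets a washout of 7 to 14 days from the last dose, with a +2 day allowance. On the tabulated days, last doses fall on Days 14 and 39 and the next first doses on Days 26 and 51. SAP 7.2, like Protocol 11.5.2, says: "Any adverse events that started during a washout period will be assigned to the treatment period just prior to that washout period". The SAP sets no end to the treatment-emergent window and plans no exposure-adjusted rate.

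**After Day 65.** Section 9.1 has subjects report later events believed related to treatment. "This information must be recorded in the Investigator's source documents", and only serious ones go on to the sponsor. Section 7.1 adds a call: "All subjects should have a safety follow-up call conducted 30 days after last visit". Its content stays in source, except that serious adverse events (SAEs) are reported as Section 9.2 describes.

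**Pharmacology.** From an effective half-life of 40 to 56 h, Section 3.2 concludes that the maximum washout "would need to be approximately 12 days".

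**SAE end dates.** Section 9.2.2 and footnote 21 of Table 8-1 use 30 days after the last dose of investigational product. After that: "Any SAEs experienced after this period should only be reported to Novartis if the investigator suspects a causal relationship to study treatment". For subjects who have stopped treatment, Section 7.2 lists AEs and SAEs among the items for which "the following data should be collected at clinic visits or via telephone/email contact until" the end of study visit.

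**The concern.** One attribution rule gives each treatment a nominal 12 days of post-dose observation in two periods and 1 day in the third. The by-treatment tables therefore pool exposures watched for different lengths of time without saying so. A non-serious event that begins two days after the last dose is counted if the dose was in Period 1 or 2. If the dose was in Period 3, it is not.

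Safety and tolerability of each salt is a secondary objective (Protocol 2.2), and Section 1.4 says the data are to support bridging to the maleate safety database. A reader using these tables for bridging will look at the absolute incidence per treatment as well as the difference from placebo, and the short window lowers the absolute figure. The sponsor already plans to speak to every subject after Day 65, so part of the missing information is asked for but not analysed.

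A related wording problem is that Sections 7.1, 7.2 and 9.2.2 give different end points for SAEs, which matters for subjects who stop treatment early and remain in the study.

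**Working it through.** **1. The plan's own figures.**
- Washout (3.2): 5 × 56 / 24 = 11.7 days, which the protocol rounds to 12. Reproduced.
- Sample size (11.7): 42 / 0.80 = 52.5, so 53, rounded up to a multiple of six = 54, or 9 per sequence. Reproduced.

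**2. Share of exposures in Period 3.** In Table 6-2 each treatment stands in Period 3 in 2 of 6 sequences: 2 × 9 = 18 of its 54 planned exposures, 33%. If 12 of 54 subjects leave:
- all just before Period 3: 42 / (54 + 54 + 42) = 28%
- all before Period 2: 42 / (54 + 42 + 42) = 30%

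**3. Window lengths.** Let w be the days from the last dose to the next period. The AE window is 13 + w days in Periods 1 and 2, and 13 + 1 = 14 days in Period 3. With equal numbers in each period, the missing share is (w − 1) / 3w of post-dose days and (w − 1) / [3(13 + w)] of the whole window.

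| w (days) | Window, Periods 1 and 2 | Window, Period 3 | Post-dose days missing | Whole window missing |
|---|---|---|---|---|
| 7 | 20 | 14 | 6/21 = 28.6% | 6/60 = 10.0% |
| 12 (nominal) | 25 | 14 | 11/36 = 30.6% | 11/75 = 14.7% |
| 14 | 27 | 14 | 13/42 = 31.0% | 13/81 = 16.0% |
| 16 (14 + 2) | 29 | 14 | 15/48 = 31.2% | 15/87 = 17.2% |

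In person-days for 42 completers (14 exposures per treatment and period, nominal schedule): 14 × (12 + 12 + 1) = 350, against 14 × 36 = 504 with equal windows. The shortfall is 154/504 = 30.6%.

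**4. Effect of attrition.** At w = 12 the post-dose shortfall is the Period 3 share × 11/12, and the whole-window shortfall is that share × 11/25. At 28% these are 25.7% and 12.3%; at 30.4% they are 27.9% and 13.4%. This treats every started period as having its full window.

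**5. SAE end dates (nominal days).**
- Completer: 64 + 30 = Day 94 from last dose; 65 + 30 = Day 95 from last visit. The gap is one day.
- Treatment stopped on Day 14, last visit Day 65: Day 44 under 9.2.2, Day 65 under 7.2, Day 95 under 7.1.
- Treatment stopped on Day 14, last visit Day 15: Day 44 under 9.2.2, Day 45 under 7.1.

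Which early-stopper case applies is unclear. Section 7.2 first says that such subjects are withdrawn from the trial, and later that they are not considered withdrawn unless they withdraw consent.

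**The case against.** **Balance.** The safety objective is comparative, and Table 6-2 places acetate, maleate and placebo in Period 3 equally often. A reader might infer that the short window biases one treatment against another; the documents do not support that. Nor does the plan include a period or sequence breakdown of AEs that the unequal windows would distort: the summaries are descriptive and by treatment. This objection stands and limits the point to absolute incidence.

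**Denominator.** The 31% refers only to post-dose, off-treatment days. Over the whole AE window the figure is about 15%. Both belong in the report.

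**Pharmacology.** A reader might compute 2^(−24/40) = 0.66 to 2^(−24/56) = 0.74 and infer that two thirds or more of the drug remains when collection closes. That assumes mono-exponential decline, whereas Protocol 1.3.2.1 describes a multiphasic one. Section 3.2 also puts the FEV₁ effect at roughly 48 h, and Section 1.1 describes post-inhalation cough as rapid in onset and short-lived. The documents name no delayed reaction that would be missed. The 12 days serve here only as the protocol's own washout figure.

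**Other safeguards.** Events already detected are followed to resolution, everyone is called, and SAEs are reportable for 30 days after the last dose. The gap is therefore confined to new non-serious events after Day 65.

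**SAEs.** A reader might infer that sites may properly omit SAEs that 7.1 and 7.2 require. That goes too far. Section 7.1 defers to 9.2, Section 7.2 concerns collection rather than expedited reporting, and 9.2.1 puts all AEs on the CRF. What stands is that the end date for early stoppers who remain in the study, and the timing of their last visit, are not settled.

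**Conclusion.** The point holds as a limited one. Post-dose AE collection is about 1 day in Period 3 against 7 to 16 days (nominally 12) after Periods 1 and 2, and this affects 28% to 33% of each treatment's exposures, depending on attrition. With equal numbers per period on the nominal schedule, about 31% of post-dose follow-up and 15% of the whole AE window are missing per treatment. The whole-window figure ranges from 10% to 17% with washout length, and attrition before Period 3 lowers both figures somewhat.

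These are shares of observation time, not of events. How many events are missed depends on how often non-serious events begin after the last dose, which the documents do not give. The tables will understate absolute late non-serious incidence and mix window lengths. The discrepancy in SAE end dates is one day for completers; for early stoppers it depends on a last visit that the protocol leaves unclear.

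**What to change.** 1. **Record late Period 3 events.** In Protocol 9.1 and 7.1, enter on the AE CRF all AEs with onset up to 12 days after the last Period 3 dose (nominally Day 64 + 12 = Day 76), asked about at the planned call. In SAP 7.2, assign them to the Period 3 treatment. No new visit is needed. The costs are CRF entry, a possibly later data cut because call data now stay in source, and weaker recall: the call falls nominally on Day 95, 19 days after that window closes, whereas Period 1 and 2 washout events are asked about on site. A fixed 12 days also does not match an actual washout of 7 to 16 days, so this step alone does not equalise ascertainment.

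2. **Add a common-window summary.** In SAP 7.2, add a supportive AE table by treatment that uses the same window in every period, from first dose to about 24 h after the last dose of that period. It needs no new data. It leaves out washout events, so it supplements the main table and does not replace it.

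3. **Reconcile the SAE text.** Align Sections 7.1, 7.2 and 9.2.2 and footnote 21 of Table 8-1 so that one SAE reporting end date applies to subjects who stop treatment early but remain in the study, and state when their end of study visit falls. The cost is a wording change.
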